If this research is hypothesis driven, succinctly state the hypothesis:

The intraoperative administration of NS will result in an increase in the base deficit when compared to LR or Normosol-R resuscitation.

Outline the major steps and methodologies in the clinical protocol. If necessary, include a description of any procedures being performed already for diagnostic or treatment purposes.

Inclusion would be:

10-21 years of age

Major surgical procedure requiring arterial access

Exclusion criteria:

Comorbid disease process that contraindicates the use of any of the 3 crystalloid solutions.

The only variable that will be altered for the purpose of the study is the fluid used for intraoperative resuscitation. Although all 3 fluids are commonly used, the choice is based on the discretion of the attending anesthesiologist. For the purpose of this study, randomization will occur so that intraoperative fluid resuscitation/administration will include one of 3 isotonic fluids: NS, LR or Normosol-R.

The anesthetic technique will follow our routine standardized anesthetic for posterior spinal fusion. Premedication will include oral or intravenous midazolam following by anesthetic induction to including either inhalational or intravenous induction. As per our usual routine, two peripheral intravenous cannulas and an arterial cannula will be placed. Maintenance anesthesia will include desflurane (inspired concentration adjusted to maintain the bispectral index at 50-60) and a sufentanil or remifentanil (infusion up to 0.3 µg/kg/hour for sufentanil or 0.3 µg/kg/hour) to maintain the mean arterial pressure at 50-65 mmHg. Additional opioids such as morphine, hydromorphone or methadone may be administered according to the clinical plan per the attending anesthesiologist. Labetolol (0.1-0.15 mg/kg/dose) will be administered as needed to control the MAP if the sufentanil infusion is not effective. Fluid will be administered as clinically indicated based on clinical parameters including heart rate, blood pressure, and urine output. As clinically indicated, arterial blood gas and electrolytes will be analyzed using the point-of-care monitoring (I-stat). At this time, we will also run for lactate values. This is generally obtained 2-4 times during these cases. We will be recording the pre and post Cobb Angle, levels fused of spine, region of spinal fusion, and instrumentation.

Identify the variables to be measured and how they will be statistically evaluated: The primary outcome variable is base deficit. Secondary outcomes include electrolyte values, lactate values, intraoperative fluid requirements, and intraoperative urine output. The primary hypothesis of the study will be evaluated using measurements obtained after administration of fluid (NS, LR, or Normosol, according to randomized assignment) during each procedure. Specifically, the incidence of base deficit in excess of -2 mEq/L will be compared between NS and LR and between NS and Normosol using tests of proportions. In a pilot study enrolling 48 patients, we found that the incidence of base deficit in excess of -2 mEq/L was 15%. The study will be powered to detect an increase in incidence from 15% to 40% between NS and either LR or Normosol, with the overall Type I error set at 0.05 and the significance level of individual tests (NS vs. LR; NS vs. Normosol) adjusted for multiple comparisons using the Bonferroni correction. To attain 80% power for detecting this expected difference, two-

tailed tests of independent proportions will require 60 patients in each group. Therefore, we propose enrolling a total of 180 patients in the study, randomized equally among the 3 groups. For comparison, the proposed sample size will have >99% power to detect a -2 mEq/L difference in base deficit after fluid administration between NS and either LR or Normosol, using ANOVA with a Bonferroni correction for multiple comparisons, and assuming a standard deviation of 2.2 mEq/L based on our pilot data. Continuous data on the primary and secondary outcomes will be evaluated further using mixed effects linear models, to account for repeated measures (including any measures taken prior to fluid administration) and potential time-varying and time-invariant confounding characteristics.

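### The two primary comparisons ignore the pre-operative Cobb angle that the trial already records; pre-specified adjustment is a cheap, conditional gain in efficiency, not the repair of an error

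*Combined protocol and SAP*

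**What the plan says.** The section *Identify the variables to be measured and how they will be statistically evaluated* states: "The primary outcome variable is base deficit". The primary hypothesis is decided on a dichotomy at -2 mEq/L, whose incidence "will be compared between NS and LR and between NS and Normosol using tests of proportions". On size it says: "The study will be powered to detect an increase in incidence from 15% to 40% between NS and either LR or Normosol". The error rate over both comparisons is 0.05, and the level of each single test is to be "adjusted for multiple comparisons using the Bonferroni correction". That gives 60 patients per group and 180 in all.

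The same section sends continuous data on primary and secondary outcomes to mixed linear models as a further evaluation. Those models may include pre-fluid measurements and confounders, fixed or changing over time, but none is named.

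The section *Outline the major steps and methodologies in the clinical protocol* says: "We will be recording the pre and post Cobb Angle, levels fused of spine, region of spinal fusion, and instrumentation". Nothing states how these items will be used in the analysis.

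**The concern.** The background says that large saline volumes produce a dilutional acidosis, and the methods section gives fluid according to clinical need. A more extensive operation plausibly means more fluid and so a larger base deficit. If so, a measure of extent that is fixed before treatment carries information about the outcome, and the two deciding tests do not use it.

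What is at stake is precision. The sample size is set close to its 80% target and no allowance for unusable patients is stated, so a few points of power obtained without extra patients would be welcome. The open wording of the mixed models also leaves any covariate choice to be made after the data are seen. Naming the covariate in advance removes that freedom.

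**Working it through.** **1. Reproduce the plan's figure.** Inputs from the statistical section: 15% and 40%, 80% power, two-tailed, overall 0.05 split over two tests, hence 0.025 each.

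n = [z(0.9875)·√(2·p̄·q̄) + z(0.80)·√(p1·q1 + p2·q2)]² / (p2 − p1)², with p̄ = 0.275.

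- 2·p̄·q̄ = 2 × 0.275 × 0.725 = 0.39875, square root 0.6315
- p1·q1 + p2·q2 = 0.1275 + 0.24 = 0.3675, square root 0.6062
- n = (2.2414 × 0.6315 + 0.8416 × 0.6062)² / 0.25² = 3.708 / 0.0625 = 59.3, so **60 per group**, as stated
- Power at 60: Φ[(0.25·√60 − 1.4154) / 0.6062] = Φ(0.860) = **80.5%**. The exact power of the pooled z-test is 81.7%. The plan does not say which test of proportions it means; Fisher's exact test would have 75.1%.

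**2. Which recorded items are safe to adjust for.**

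- The pre-operative Cobb angle precedes the study fluid, so fluid assignment cannot affect it.
- The post-operative angle follows treatment.
- Levels and instrumentation are listed without saying whether planned or performed. Levels as performed are settled during the operation.

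**3. What adjustment would gain.** The share of variation explained (R²) is not in the documents, so it is assumed over a range. Simulation: one pair of arms, 60 each; a latent normal outcome with event rates of 15% and 40%; two-sided 0.025. The unadjusted pooled z-test is compared with the standardised risk difference from a logistic model with arm and one covariate. Each setting has 10,000 trials, with a Monte Carlo standard error near √(0.82 × 0.18 / 10,000) = 0.4 points. The covariate acts equally in both arms.

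| Latent R² | Unadjusted power | Adjusted power | Gain (points) |
|---|---|---|---|
| 0 | 82.34% | 82.58% | 0.24 |
| 0.05 | 81.23% | 82.88% | 1.65 |
| 0.10 | 81.98% | 84.27% | 2.29 |
| 0.20 | 82.58% | 86.71% | 4.13 |
| 0.30 | 82.00% | 88.51% | 6.51 |

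With no true difference (15% in both arms), rejection over these settings was 2.5% to 2.8% unadjusted and 2.6% to 2.9% adjusted, so the error rate is essentially unchanged.

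**4. The same design with the covariate acting only in the NS arm.** 4,000 trials per setting, logistic likelihood-ratio test.

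| Latent R² (NS arm only) | Unadjusted power | Adjusted power | Gain (points) |
|---|---|---|---|
| 0.10 | 82.0% | 82.8% | 0.8 |
| 0.20 | 82.5% | 84.0% | 1.5 |
| 0.30 | 82.4% | 83.8% | 1.4 |

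**5. How many covariates the data can carry.** Expected events are 0.40 × 60 + 0.15 × 60 + 0.15 × 60 = 24 + 9 + 9 = 42 over three arms, or 33 in one pair of arms. That supports two or three covariates.

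**The case against.** The strongest reply is that nothing is broken. An unadjusted comparison of randomised groups is valid, its error rate already covers chance imbalance, and it meets its own power target by the pooled formula. All of that stands.

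A reader might infer that the extent of surgery is known before randomisation and that power is therefore being lost. The documents support neither step. Only the pre-operative angle is clearly a pre-treatment value; planned levels are mentioned nowhere and would be a new item. No passage links the angle or the levels to base deficit, so the loss may be nil.

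The mechanism also works against the larger gains. The background says that the dilutional acidosis does not occur with LR or Normosol. If extent acts only through saline volume, it predicts events mainly in the NS arm, where the gain is about 1 point. This is a limiting case, since surgery may affect base deficit by other routes, but it means that the equal-effect table cannot be read as the expected result.

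Two further points stand in part. The continuous primary variable already goes to models that can carry covariates, and the plan gives the unadjusted continuous comparison more than 99% power; but those analyses do not decide the primary hypothesis. Pre-fluid base deficit would be a more direct covariate, but the plan refers only to any such measures that were taken and draws blood gases when clinically indicated, so it cannot be relied on for every patient.

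**Conclusion.** The point holds as an optional improvement in efficiency. The primary comparisons are unadjusted, one suitable baseline value is already collected, and pre-specified adjustment for it does essentially no harm if it proves uninformative. The size is conditional on an unstated prognostic strength: no gain at R² = 0, about 1 point of power if the covariate acts only in the NS arm, and about 2 to 7 points at latent R² of 0.10 to 0.30 if it acts equally in both arms. These figures assume a single covariate with a normal latent outcome and the plan's rates of 15% and 40%. It would go too far to call the planned test biased, invalid or underpowered for omitting covariates.

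**What to change.** Pre-specify, before any outcome data are seen:

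- **Primary analysis:** a logistic model for the existing dichotomy with arm and pre-operative Cobb angle, reporting the standardised risk difference for NS vs LR and NS vs Normosol, each at the planned 0.025 level.
- **Non-fusion cases:** eligibility covers any major procedure requiring arterial access, so the angle may not exist for some patients. Treat them as their own category.
- **Levels:** add the number of levels only if the planned value is noted before randomisation.
- **Exclusions:** do not adjust for the post-operative Cobb angle or for levels as performed.
- **Sensitivity analysis:** keep the unadjusted tests of proportions.

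The cost is a few lines of analysis wording and, if levels are used, one new item to record. No extra patients are needed. The limitation is the small number of events, which caps the list at two or three covariates.

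### The mixed models are to adjust a randomised fluid comparison for time-varying confounders; variables measured after fluid starts cannot confound it, and adjusting for one the fluid changes alters what the arm coefficient estimates

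*Combined protocol and SAP*

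**What the plan says.** The protocol's methods section (*Outline the major steps and methodologies in the clinical protocol*) makes assignment random: "randomization will occur so that intraoperative fluid resuscitation/administration will include one of 3 isotonic fluids: NS, LR or Normosol-R". It adds that fluid is the only thing altered for the study.

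The statistical section (*Identify the variables to be measured and how they will be statistically evaluated*) describes two layers of analysis.

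- **Primary.** The incidence of base deficit beyond the -2 mEq/L threshold "will be compared between NS and LR and between NS and Normosol using tests of proportions". No covariates are mentioned.
- **Further.** "Continuous data on the primary and secondary outcomes will be evaluated further using mixed effects linear models". These are to handle repeated measures, including any taken before fluid, and "potential time-varying and time-invariant confounding characteristics".

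The same section lists the other outcomes: "Secondary outcomes include electrolyte values, lactate values, intraoperative fluid requirements, and intraoperative urine output". No other analysis is described for them. For continuous base deficit, ANOVA appears only in the power statement ("using ANOVA with a Bonferroni correction for multiple comparisons, and assuming a standard deviation of 2.2 mEq/L based on our pilot data").

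No covariate is named for the mixed models, and nothing limits the time-varying ones to variables the fluid cannot affect. On sampling, the methods section says: "As clinically indicated, arterial blood gas and electrolytes will be analyzed using the point-of-care monitoring (I-stat"), generally two to four times per case, with lactate run at the same time.

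**The concern.** A confounder of the arm comparison has to be a common cause of assignment and outcome. Under randomisation, a variable measured after fluid starts cannot cause the assignment, so the stated reason for adjusting does not apply to it. If the fluid changes that variable, conditioning on it removes whatever part of the effect runs through it. It can also introduce bias where an unmeasured factor drives both the covariate and the outcome. Either way the coefficient stops answering the stated objectives, which ask for differences according to the fluid used.

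Several quantities followed during the case are outcomes in their own right: lactate, electrolytes, fluid volume and urine output. Lactate is a natural candidate covariate for base deficit. The background says a serum lactate may be needed to separate poor perfusion from saline dilution, and it lists lactate as the buffer in LR.

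For fluid volume, the methods section guides administration by clinical parameters that include heart rate, blood pressure and urine output. The significance section suggests acid-base status may also influence resuscitation. A route from fluid type to volume given is therefore plausible, but not shown.

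At stake are the secondary comparisons. A fluid effect could be partly adjusted away, or could appear where the total effect is nil, with no other prespecified analysis to reveal it.

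**Working it through.** **Inputs from the plan.** 60 per arm; 15% versus 40%; overall two-sided 0.05 split over two comparisons (0.025 each); 80% power; base-deficit SD 2.2 mEq/L and difference 2 mEq/L.

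**Assumed inputs.** r is the covariate's within-arm correlation with the outcome, from any source. d is its between-arm mean difference in SDs. The documents give neither. A two-sided 0.05 level is also assumed, because the plan sets none for secondary outcomes.

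**1. The plan's own sample size.** With pooled variance and no continuity correction:

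n = [2.241 × √(2 × 0.275 × 0.725) + 0.842 × √(0.15 × 0.85 + 0.40 × 0.60)]² / 0.25² = 59.3, rounded up to 60.

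This reproduces the stated figure. Power for 2 mEq/L at SD 2.2 is 99.7%, consistent with the stated value above 99%. Neither figure depends on the mixed models.

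**2. Unadjusted precision.** SE = √(2/60) = 0.183 SD, or 0.183 × 2.2 = 0.40 mEq/L for base deficit.

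**3. Effect of adjusting, one value per patient.**

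- Shift in the arm estimate = r × d outcome SDs, in either direction.
- Adjusted SE = 0.183 × √[(1 − r²)(1 + d²/4)].

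| r | d | Shift (SD) | Adjusted SE | Shift / adjusted SE | False positives, zero total effect |
|---|---|---|---|---|---|
| 0.3 | 0 | 0 | 0.174 | 0 | 5.0% |
| 0.3 | 0.25 | 0.075 | 0.176 | 0.43 | 7.1% |
| 0.3 | 0.5 | 0.150 | 0.180 | 0.84 | 13.3% |
| 0.5 | 0.25 | 0.125 | 0.159 | 0.78 | 12.3% |
| 0.5 | 0.5 | 0.250 | 0.163 | 1.53 | 33.5% |

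Least-squares simulation (20,000 runs) gave 7.1%, 12.2% and 32.7% for (r, d) = (0.3, 0.25), (0.5, 0.25) and (0.5, 0.5).

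If the total effect is 0.5 SD and the shift is towards zero, power falls from 78.2% to 67.8% for (0.3, 0.25) and to 33.5% for (0.5, 0.5).

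**4. Repeated measures.** The planned model is a mixed model, so the check was repeated with random intercepts, 2 to 4 draws per patient and an assumed intraclass correlation of 0.5 (2,000 runs). Adjusted false positives were 9.7%, 15.9% and 48.9% for (0.3, 0.25), (0.5, 0.25) and (0.5, 0.5), against 4.6% to 5.3% unadjusted. With r = 0.5 and d = 0 the rate stayed at 5.2%. The one-value table therefore does not overstate the problem under these assumptions.

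**5. Base deficit at the planned difference.** The smallest and largest shifts are 2.2 × 0.075 = 0.165 and 2.2 × 0.25 = 0.55 mEq/L. The worst case leaves 2 − 0.55 = 1.45 mEq/L. That is 1.45 / (2.2 × 0.163) = 4.0 adjusted SEs from zero (3.6 on the unadjusted SE), so the conclusion would not reverse.

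**6. What is given up by not adjusting.** For a covariate the fluid does not affect (d = 0), r = 0.5 gives SE = 0.183 × √0.75 = 0.158. Power for a 0.5 SD effect is then about 88%, against 78% without the covariate. At r = 0.3 it is 82%.

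**The case against.** The strongest reply is that the harm is conditional. The plan says potential, names no covariate, and nowhere says that lactate, electrolytes, volume or urine output will be adjusted for. That stands. A reader might infer that the planned models are biased, or that the authors intend to condition on their own outcomes; the text supports neither. Some quantities that vary during the case, such as anaesthetic, opioid and labetalol use, are not said to respond to the fluid. Adjusting for those may do no harm and may gain precision.

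A second reply is that clinically triggered draws justify time-varying covariates. Randomisation protects the comparison of patients, but not automatically the comparison of whichever samples happened to be taken. The number and timing of draws follow randomisation and could respond to the fluid. This also stands, and it means time of draw cannot simply be called harmless. But it is a problem of informative observation, not confounding of assignment. It supports a labelled sensitivity analysis, not a change in what the main coefficient estimates.

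A third reply is that time-varying may mean no more than time since start. The wording is confounding characteristics, which is broader than elapsed time.

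**Conclusion.** The point holds in conditional form. The plan states an adjustment rule that randomisation does not call for and that permits covariates the fluid may change. Following it could change the estimand in the only analysis described for the secondary outcomes and in the supporting model for continuous base deficit. That is more than a missing covariate list.

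The documents give no basis for the size or direction of any shift. Over the assumed range, the one-value-per-patient shift is 0.075 to 0.25 SD, with false positives of 7% to about 33%. It is zero if the covariate does not differ by arm or is unrelated to the outcome.

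It would be wrong to infer that the trial's main conclusion is at risk. The primary tests of proportions carry no such adjustment, the sample size reproduces, and within this range the continuous base-deficit result would survive at the planned 2 mEq/L. The change should be made, but it is not critical to the trial.

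**What to change.** In the models that estimate the fluid effect:

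- Replace adjustment for time-varying confounders with adjustment only for named characteristics fixed before fluid starts, plus time of draw. The plan records spinal variables ("We will be recording the pre and post Cobb Angle, levels fused of spine, region of spinal fusion, and instrumentation") without proposing them as covariates. If they are used, the post-operative Cobb angle does not qualify, and the others do only if fixed before fluid.
- Keep any pre-fluid value of the outcome as a repeated response with a common mean across arms, so that patients without one are not dropped.
- State one arm contrast as the fluid effect, for example the average difference over post-fluid draws. This is essential if an arm-by-time term is included, because the arm coefficient alone is then not a single overall effect.
- Where fluid volume and urine output are per-case totals, compare one value per patient with the same pre-fluid covariates.
- State that the main model assumes draw timing is uninformative given arm and pre-fluid covariates.

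Models with post-fluid covariates may be kept as labelled exploratory or sensitivity analyses, including for clinically triggered draws or for studying base deficit as a marker of resuscitation. They should not be reported as the fluid effect.

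The cost is analysis wording, with no extra patients or data. The downside is the possible loss of precision shown in step 6 of the working.
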